### **6.3 Unblinding Procedures (Code break)**

The Principal Investigator will be informed on the randomization and will be available 24/24 hours, 365 days/year in case of complications related to the pudendal nerve block occur. In case of serious complications also the authorized personnel (physician responsible for the study, the anaesthetist and the surgeons) will have the possibility to access to the randomization, the principal investigator will be always get informed.

## **7. STUDY POPULATION**

### **7.1 Eligibility criteria**

Inclusion criteria:

- Patients affected by haemorrhoids (grade III and IV) and treated with Milligan-Morgan hemorrhoidectomy under spinal anaesthesia
- Signed informed consent

Exclusion criteria:

- Age < 18 years old

- Pregnancy
- Allergy to local anaesthetics

## **7.2 Recruitment and screening**

The population recruitment will be at the Proctology Consulting Room, ORBV Bellinzona.

## **7.3 Assignment to study groups**

The randomization list will be created by the CTU-EOC and the randomization will be performed by the authorized personnel (physician responsible for the study, the anaesthetist and the surgeons) of the participating centre via RedCap®. Only the physician responsible for the study, the anaesthetist and the surgeons will be informed about the treatment arm.

## **7.4 Criteria for withdrawal / discontinuation of participants**

Participants are withdrawn from the study in case of informed consent not signed or non-compliance to the treatments.

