### **2.7 Patient Information and Informed Consent**

All patient will receive an informed consent to participate to the study.

The investigators will explain to each participant the nature of the study, its purpose, the procedures involved, the expected duration, the potential risks and benefits and any discomfort it may entail. Each participant will be informed that the participation in the study is voluntary and that he/she may withdraw from the study at any time and that withdrawal of consent will not affect his/her subsequent medical assistance and treatment.

The participant must be informed that his/her medical records may be examined by authorised individuals other than their treating physician.

All participants for the study will be provided a participant information sheet and a consent form describing the study and providing sufficient information for participant to make an informed decision about their participation in the study.

The patient information sheet and the consent form will be submitted to the CEC and to the competent authority to be reviewed and approved. The formal consent of a participant, using the approved consent form, must be obtained before the participant is submitted to any study procedure.

The participant should read and consider the statement before signing and dating the informed consent form, and should be given a copy of the signed document. The consent form must also be signed and dated by the investigator (or his designee) and it will be retained as part of the study records.

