## **8. STUDY INTERVENTION**

### **8.1 Identity of Investigational Products**

#### **8.1.1 Experimental Intervention**

After patients select and randomization:

Group A will undergo pudendal nerve block under ultrasonographic control with injection of 10 mls of ropivacaine 0.75. Group B will receive no treatment.

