#### **8.4 Data Collection and Follow-up for withdrawn participants**

Results will be collected on specific printed formularies (CRFs). The Principal Investigator will preserve the sensitive data in his office in a closed cabinet key. Results will be then collected on a Redcap® electronic database. The access to the database will require username and password. Only the authorized personnel (physicians responsible for the study) will have the access rights and all changes on the database are trackable.

[figure not shown]
In-patients will be then controlled after 1 months and out-patients will be controlled after 1 and 4 weeks.

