#### **8.5 Concomitant Interventions (treatments)**

No specific or relevant concomitant care or treatment are allowed.

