### **9.2.4 Assessments in participants who prematurely stop the study**

Participants can be withdrawn from the study prematurely in case of adverse events after the pudendal nerve block.

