#### **11.3.1 Datasets to be analysed, analysis populations**

All randomized subject will be included in the analyses

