### **11.4 Handling of missing data and drop-outs**

In case of missing data, the patient will be dropped-out. 2 drop-outs each arm is planned

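### Mandatory withdrawal for undefined non-compliance (7.4), combined with the rule that drops patients with missing data (11.4), conflicts with the promise to analyse all randomised patients (11.3.1) and can remove patients unevenly by arm

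*Combined protocol and SAP*

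**What the plan says.** Five sections of the combined protocol and SAP bear on who remains in the primary comparison.

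- **7.4 (withdrawal criteria):** "Participants are withdrawn from the study in case of informed consent not signed or non-compliance to the treatments". The wording is mandatory and refers to leaving the study, not only the treatment. It does not define non-compliance or say who judges it.
- **9.2.4 (premature stop):** "Participants can be withdrawn from the study prematurely in case of adverse events after the pudendal nerve block".
- **8.4 (headed as data collection and follow-up for withdrawn participants):** it covers data handling and later visits: "In-patients will be then controlled after 1 months and out-patients will be controlled after 1 and 4 weeks". It does not mention VAS at 6 to 48 hours.
- **11.4 (missing data):** "In case of missing data, the patient will be dropped-out. 2 drop-outs each arm is planned".
- **11.3.1 (analysis population):** "All randomized subject will be included in the analyses".

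On treatment, Group A receives the block, while 8.1.1 says "Group B will receive no treatment". Both arms receive the same postoperative analgesic regimen, with opioids as needed (8.1.2). Section 8.5 adds: "No specific or relevant concomitant care or treatment are allowed".

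**The concern.** Compliance is observed after randomisation, so a rule that removes patients for non-compliance can undo the balance that randomisation created. Here one route into non-compliance, a block not done or not completed, exists only in Group A. So does the adverse-event route in 9.2.4. In either arm, treatment outside the regimen could be read as non-compliance because of 8.5, and for a pain endpoint it is plausible that this goes with more pain.

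The timing matters. A block that is not done is known before the first VAS reading at 6 hours. The common regimen runs for at least 24 hours in 8.1.2 and at least 48 hours in the synopsis (the two need reconciling). Non-compliance with it can therefore arise inside the primary outcome window. A patient withdrawn then may have no further VAS, and the reading cannot be recovered later. With 20 per arm, a few selective losses are enough to move the result.

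**Working it through.** **1. How the rules combine.** Withdrawal under 7.4 or 9.2.4, with no provision in 8.4 for further VAS, leaves missing readings. Section 11.4 then drops the patient, against 11.3.1. The exclusion comes from 11.4; 7.4 creates the missing data.

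**2. The plan's own figures (11.2, 11.4).** 18 evaluable per group and 10% drop-out: 18 / (1 − 0.10) = 20 per group. This matches the plan, as do the 2 planned drop-outs per arm.

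**3. The implied effect.** The plan gives a 33% reduction in VAS but no SD or control mean, so the 18 cannot be checked directly. Solving the two-sample t-test for 18 per group, two-sided 0.05 and power 0.80 gives a standardised effect of 0.96 SD. For a 33% reduction, that means an SD of 0.33 / 0.96 = about 34% of the control mean. With all 20 per group analysed, power at this effect is 84%.

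**4. What selective loss could do.** Assumptions: 20 per arm, one normally distributed score per patient, t-test, 100,000 simulated trials. The losses below are assumed; the documents do not predict them.

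| Who leaves | Shift in difference | Two-sided type I error | Power at 0.96 SD |
|---|---|---|---|
| Nobody | 0 | 5% | 84% |
| Two from one arm, unrelated to pain | 0 | about 5% | 82% |
| Two worst-pain patients from each arm | 0 | about 8% | 88% |
| Two worst-pain patients from A only | 0.18 SD towards the block | about 10% (about 9% favouring the block) | not a loss of power: the effect is exaggerated |
| Two worst-pain patients from B only | 0.18 SD against the block | about 10% | 69% |

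Check on the shift: the two highest of 20 standard normal values average about 1.64. Removing them lowers the mean of the remaining 18 by 2 × 1.64 / 18 = 0.18 SD.

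A weaker link gives less. With a correlation of 0.5 between withdrawal and pain, two losses from one arm shift the difference by about 0.09 SD, with type I error about 6%.

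**5. Cost of keeping everyone.** If two of the 20 blocks have no effect and those patients stay in Group A, the average effect is 0.96 × 18/20 = about 0.86 SD and power is about 0.74 to 0.75. Excluding those two patients would give about 0.82.

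**The case against.** A reader might infer that 7.4 by itself breaks the randomised comparison and that 11.3.1 cannot be met. The documents do not go that far. Section 7.4 excludes nobody from the analysis. A withdrawn patient with all VAS readings to 48 hours could still be analysed, and 8.4 is silent on those readings; it does not forbid them.

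Three further inferences are also unsupported as facts.

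- **Dependence on pain.** This is plausible but not stated. Opioids as needed are inside the regimen, so a patient in severe pain has relief without breaching 8.5.
- **Assessors who know the arm.** Sections 6.2.1 and 6.2.2 say who knows the allocation. No section says who judges compliance.
- **A block not done as non-compliance.** Whether an incomplete block counts under 7.4 depends on a definition that the plan does not give.

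The size is also open to challenge. Under the null the block has no effect, so a failed block adds no pain and its removal alone does not raise the error rate. Two losses per arm is what 11.4 plans, but the 10% and 69% figures need both worst-pain patients to come from one arm and none from the other. Part of the fall to 69% is lost sample: two random losses from Group B alone give 82%. The t-test also simplifies the planned repeated-measures analysis in 11.3.

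The unsigned-consent ground in 7.4 adds no bias. Section 2.7 already says that consent "must be obtained before the participant is submitted to any study procedure", and 7.1 makes it an inclusion criterion.

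These objections limit the claim to a possible bias of uncertain size. They do not remove the conflict between 7.4 with 11.4 and 11.3.1, or the two withdrawal routes that only Group A has.

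**Conclusion.** The point holds as a conflict between sections and a risk of bias. As written, 7.4 and 9.2.4 can take patients out after randomisation, 8.4 does not secure their VAS, and 11.4 then drops them, so 11.3.1 cannot be relied on. Losses can differ by arm because of the block, and plausibly with pain.

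Under the stated assumptions the shift runs from none (withdrawal unrelated to pain, or alike in both arms) to 0.18 SD (the two worst-pain patients lost from one arm only), against an implied design effect of 0.96 SD. Type I error runs from about 5% to about 10%, and power could fall to 69% if Group B bears the loss. Nothing in the documents says where in this range the trial would fall. It is worth correcting because uncollected readings cannot be recovered and the correction is cheap.

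**What to change.** - **7.4 and 9.2.4:** separate stopping or not receiving study treatment from leaving the study. Define non-compliance. Record it, a block not done or incomplete, and non-protocol treatment as protocol deviations.
- **8.4:** state that VAS is collected to 48 hours in all randomised patients unless the patient withdraws consent to data collection.
- **11.3.1:** add that patients are analysed in the allocated arm.
- **11.4:** amend so that these patients are not dropped for a missing reading, and use the VAS readings available.
- **Sensitivity analysis:** a per-protocol set may be shown, labelled as such.

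The unsigned-consent wording in 7.4 can be tidied at the same time.

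The cost is a short amendment, with the ethics committee approval that 2.3 requires, and a deviation line on the CRF. No more patients are needed: analysing all 40 gives about 84% power at the implied effect if it is not diluted. The downside is dilution if blocks fail: with two zero-effect blocks among 20, power is about 0.74 to 0.75.

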## **8. STUDY INTERVENTION**

### **8.1 Identity of Investigational Products**

#### **8.1.1 Experimental Intervention**

After patients select and randomization:

Group A will undergo pudendal nerve block under ultrasonographic control with injection of 10 mls of ropivacaine 0.75. Group B will receive no treatment.

#### **8.1.2 Control Intervention**

In the postoperative period all the patients will receive metronidazole 500 mg x3 + paracetamol 1 gr x4 + NSAID + opioids as needed for at least 24 hours. Opioids used will be “strong opioids” (Pethidine 50 mg sc or Oxycodone Kaps 5 mg)

### **8.2 Administration of experimental and control interventions**

#### **8.2.1 Experimental Intervention**

The pudendal nerve block will be done as follow before the spinal anaesthesia:

Ultrasonography allows the visualization of important landmarks: the ischial spine, pudendal artery, sacrospinous ligament, sacrotuberous ligament and pudendal nerve. It also allows real-time needle advancement and confirmation of injectate spread within the interligamentous plane. A low frequency 2-5 MHz curved array ultrasound probe is used. After skin preparation with Povidoneiodine and sterile probe preparation within a transparent plastic sheath, scanning is performed in transverse planes to visualize the ischium forming the lateral border of the sciatic notch. By moving the ultrasound probe in a cephalad-caudal direction, the ischium appears as a progressively lengthening hyperechoic line that is widest at the ischial spine level. The ischium is initially seen as a curved line as it forms the posterior aspect of the acetabulum. When the probe is at the ischial spine level, the ischium will appear as a straight line. At this level, a colour Doppler is used to localize the internal pudendal artery pulsations in close proximity to the ischial spine. Another arterial pulsation is often seen lateral to the tip of the ischial spine and is accompanied by the sciatic nerve. This is the inferior gluteal artery. Mistaking this artery for the pudendal artery will result in sciatic nerve block. The sacrospinous ligament appears as a hyperechoic line in continuity with the ischial spine, with lower echogenicity than bone. Similarly, the sacrotuberous ligament is seen as a light hyperechoic line deep within gluteus maximus muscle and appears parallel and superior to the sacrospinous ligament in ultrasound images. Localization of the pudendal nerve is targeted in the plane between these 2 ligaments. Under ultrasound guidance, a peripheral nerve stimulating needle is inserted from the medial aspect of the probe. It is advanced in line with the ultrasound probe to the medial aspect of the internal pudendal artery. Once the needle passes through the sacrotuberous ligament, a “click” is usually felt and a small volume (1 – 2 mL) of local anaesthetic is injected. The solution appears as a hypoechoic collection, in order to identify the plane between the sacrotuberous and the sacrospinous ligaments and to accentuate the pudendal nerve appearance (pudendal nerve however is not always visible). The needle is inserted medially toward the pudendal artery as the pudendal nerve is principally located medial to this artery. 10 mls of ropivacaine 0.75% are injected within this fascial plane, after negative aspiration. The procedure is then repeated identically on the contralateral side.

This procedure is usually a quite painful technique; thus, it is important to perform it after the spinal anaesthesia. It would be necessary to do it before the spinal anaesthesia just in case the pain would be associated to a nerve lesion. In this study the infiltration is not done on the nerve but in a muscular plane, thus is not needed the patient’s sensibility.

The procedure will be performed at our institution by one of the three expert anaesthesiologists in the peripheral nerves’ blockage. Those anaesthesiologists are:

- [name]. [name], Primario di Anestesia ORBV
- [name]. [name], Caposervizio Anestesia ORBV, board member of the Swiss Society of Loco-regional Anaesthesia
- [name]. [name], Caposervizio Anestesia e responsabile terapia del dolore ORBV

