
Study Product / Intervention:
	
The pudendal nerve block will be done after the spinal anaesthesia: Ultrasonography allows the visualization of important landmarks: the ischial spine, pudendal artery, sacrospinous ligament, sacrotuberous ligament and pudendal nerve. It also allows real-time needle advancement and confirmation of injectate spread within the interligamentous plane. A low frequency 2-5 MHz curved array ultrasound probe is used. After skin preparation with Povidoneiodine and sterile probe preparation within a transparent plastic sheath, scanning is performed in transverse planes to visualize the ischium forming the lateral border of the sciatic notch. By moving the ultrasound probe in a cephalad-caudal direction, the ischium appears as a progressively lengthening hyperechoic line that is widest at the ischial spine level. The ischium is initially seen as a curved line as it forms the posterior aspect of the acetabulum. When the probe is at the ischial spine level, the ischium will appear as a straight line. At this level, a colour Doppler is used to localize the internal pudendal artery pulsations in close proximity to the ischial spine. Another arterial pulsation is often seen lateral to the tip of the ischial spine and is accompanied by the sciatic nerve. This is the inferior gluteal artery. Mistaking this artery for the pudendal artery will result in sciatic nerve block. The sacrospinous ligament appears as a hyperechoic line in continuity with the ischial spine, with lower echogenicity than bone. Similarly, the sacrotuberous ligament is seen as a light hyperechoic line deep within gluteus maximus muscle and appears parallel and superior to the sacrospinous ligament in ultrasound images. Localization of the pudendal nerve is targeted in the plane between these 2 ligaments. Under ultrasound guidance, a peripheral nerve stimulating needle is inserted from the medial aspect of the probe. It is advanced in line with the ultrasound probe to the medial aspect of the internal pudendal artery. Once the needle passes through the sacrotuberous ligament, a “click” is usually felt and a small volume (1 – 2 mL) of local anaesthetic is injected. The solution appears as a hypoechoic collection, in order to identify the plane between the sacrotuberous and the sacro-spinous ligaments and to accentuate the pudendal nerve appearance (pudendal nerve however is not always visible). The needle is inserted medially toward the pudendal artery as the pudendal nerve is principally located medial to this artery. 10 mls of ropivacaine 0.75% are injected within this fascial plane, after negative aspiration. The procedure is than repeated identically on the contralateral side.

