## **6. STUDY DESIGN**

### **6.1 General study design and justification of design**

This study is a randomized control single blind trial.

Patient will be randomized: Group A will undergo the pudendal nerve block under ultrasonographic control with injection of 10 mls of ropivacaine 0.75% before the spinal anaesthesia.

The population include patients with haemorrhoids (grade III and IV)

The study is single blind: an expert from the anaesthesiology team will perform the nerve block, the surgeon will be informed about the group of randomization. The nursing personnel (blinded) or the patient itself on specific formularies will evaluate the VAS scale at 6, 12, 24, 48 hours.

The comparator is no treatment

The method of randomization will be created by the CTU-EOC and the randomization will be performed by the authorized personnel (physician responsible for the study, the anaesthetist and the surgeons) of the participating centre via RedCap®. Only the physician responsible for the study, the anaesthetist and the surgeons will be informed about the treatment arm.

The expected duration of the study is 2 years, 100 patients.

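### Sections 3.3, 6.1 and 8.2.1 place the pudendal block before the spinal, while the synopsis and the protocol's only reasoning on order place it after

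*Combined protocol and SAP*

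**What the plan says.** Three sections put the block first. Sections 3.3 and 8.2.1 share the lead-in "The pudendal nerve block will be done as follow before the spinal anaesthesia". The Group A sentence in section 6.1 describes the block "with injection of 10 mls of ropivacaine 0.75% before the spinal anaesthesia".

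The synopsis, under Study Product / Intervention, says the opposite: "The pudendal nerve block will be done after the spinal anaesthesia".

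One paragraph argues the order. It is printed three times, in the synopsis and towards the end of 3.3 and 8.2.1. Its conclusion is "This procedure is usually a quite painful technique; thus, it is important to perform it after the spinal anaesthesia". It then raises a reason for the other order: "It would be necessary to do it before the spinal anaesthesia just in case the pain would be associated to a nerve lesion". It answers that reason with "In this study the infiltration is not done on the nerve but in a muscular plane", and adds that the patient's sensation is therefore not needed.

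Section 8.2.1 makes the block bilateral: "The procedure is then repeated identically on the contralateral side". Section 8.2.2 gives controls no block. Section 6.2.2 describes patients and nurses as blinded, and section 9.2.1 allows patients to record their own VAS. Section 11.2 sets 20 patients per group.

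**The concern.** Section 2.5 commits the study to being carried out according to the protocol. As written, either order departs from some section, so neither the anaesthetist nor the monitor can say which one complies. The conflicting text is not in a background remark. It opens the section that tells the anaesthetist how to give the intervention, and in section 6.1 it is the only timing given.

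The main stake is patient welfare on the protocol's own terms. Followed literally, the instruction gives patients with intact sensation a procedure that the same document calls painful, on both sides, when the spinal they are due to receive anyway could cover it.

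A secondary stake is blinding. A patient who feels two deep injections could work out the arm, since controls receive none, and the primary outcome is a subjective score that the patient may record.

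**Working it through.** Most of this check is a comparison of text. Every statement on order, side by side:

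| Place | Order | Kind of statement |
|---|---|---|
| Synopsis, Study Product / Intervention, opening | after | instruction |
| Synopsis, rationale paragraph | after | reasoning |
| 3.3, lead-in | before | instruction |
| 3.3, rationale paragraph | after | reasoning |
| 6.1, Group A sentence | before | instruction |
| 8.2.1, lead-in | before | instruction |
| 8.2.1, rationale paragraph | after | reasoning |

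1. *Count.* Before: 3 places, 2 distinct wordings (3.3 and 8.2.1 share one). After: 4 places, 2 distinct wordings (the rationale is one paragraph printed three times). The count does not decide which order is meant, because repeated text is not independent evidence.

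2. *Which order is intended.* Only one order comes with reasons. The rationale argues for after on grounds of pain, names the single argument for before (pain as a warning of nerve lesion), and says why it does not apply here (injection into a muscular plane). No section gives a reason for before that survives this. The reasoned choice is after.

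3. *Where the contradiction lies.* Sections 3.3 and 8.2.1 each open with one order and later argue for the other. Section 6.1 gives only before, with no rationale beside it to correct the reader. Section 8.1.1 is silent on order.

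4. *Size of the avoidable burden.* Inputs: 20 patients per group (11.2) and 2 sides per patient (8.2.1). The plan's own figure reproduces: 18 per group inflated for 10% drop-out is 18 / (1 − 0.10) = 20.
   - Before followed in every group A patient: 20 × 2 = 40 needle procedures with sensation intact.
   - After followed, with an effective spinal: 0.
   - The range is 0 to 40. The documents give no basis for saying where in it the trial would fall.

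5. *Effect on the statistics.* The order of block and spinal does not enter the sample-size statement in 11.2 or the comparison in 11.3, so neither changes.

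6. *Blinding.* For the order to unblind patients, three things must hold: the block is done first, sedation does not mask it, and the patient takes the sensation as a sign of the arm. The visible text says nothing about sedation and does not link order to blinding. No size or direction of any effect on VAS can be derived.

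**The case against.** The strongest reply is that the document largely settles the matter itself. In 3.3 and 8.2.1 the paragraph that argues for after follows in the same section, the synopsis says after outright, and the operators are three expert anaesthetists who would probably follow the reasoning. This stands in part: the intended order can be recovered, so the defect is one of text and not of design. It does not remove the point. Section 6.1 has no correcting paragraph, and nothing in the protocol says which sentence governs.

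A reader might infer more than the documents support, in four ways.

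- *That the protocol makes the later order mandatory.* It calls that order important, which is weaker.
- *That the primary outcome is biased.* This rests on the chain in step 6 of the working, and no link in it can be checked. The consent pages are not available for review, so what patients are told about the block is unknown.
- *That doing the block after the spinal secures patient blinding.* It removes the pain and the sensation cue. The visible text describes no sham, and whether a patient could notice the block in other ways is a separate question.
- *That the burden could be larger, because section 6.1 also says* "The expected duration of the study is 2 years, 100 patients". That figure conflicts with 20 per group in 11.2 and is a separate inconsistency. Using it would also need an assumed allocation split, so the sample-size section is the sounder basis.

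**Conclusion.** The inconsistency is real and certain from the text: three instructions give one order, while the synopsis and the only reasoning give the other. It should be fixed, because the conflicting wording opens the operative section and stands uncorrected in the design section. It is not fatal, because the intended order is clear once all the text is read together.

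The supported consequence is between 0 and 40 avoidable painful needle procedures. The upper end assumes 20 group A patients, two sides each, all blocked before the spinal. The lower end assumes the later order is followed and the spinal works. Possible unblinding of patients is a plausible inference of unknown size and direction, and the conclusion does not depend on it.

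**What to change.** Change *before* to *after* the spinal in three phrases: the lead-ins of 3.3 and 8.2.1, and the Group A sentence of 6.1. This adopts the choice that the protocol already argues for and brings all sections into line with the synopsis.

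The cost is a wording amendment. Section 2.3 requires prior approval by the sponsor and the ethics committee. Under section 2.10 a substantial amendment is implemented only after approval by the ethics committee and the competent authority, as applicable. The sponsor should decide whether a change to the timing of the intervention counts as substantial, since the protocol does not say. No extra staff, procedure or visit is needed, and the sample size and planned test stay as they are.
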